7. STATISTICAL METHODS AND DETERMINATION OF SAMPLE SIZE

7.1 STATISTICAL DESIGN - MODEL

Endpoints of this trial are given in [Section 5](#), and the trial design is described in [Section 3.1](#).

7.2 NULL AND ALTERNATIVE HYPOTHESES

It is not planned to test any statistical hypotheses in a confirmatory sense. All parameters will be evaluated descriptively.

7.3 PLANNED ANALYSES

All statistical analyses will be based on the treated set.

Treated set:

This subject set includes all subjects who received the investigational drug.

When necessary, PK/PD set may be created for PK/PD analysis, details will be described in the TSAP.

7.3.1 Primary endpoint analyses

For pharmacokinetic, and pharmacodynamic analyses, details are described in [Sections 7.3.5](#).

7.3.2 Secondary endpoint analyses

For safety, pharmacokinetic, and pharmacodynamic analyses, details are described in Sections 7.3.5.

7.3.4 Safety analyses

Safety analyses will be performed based on BI standards. Tabulations of frequencies/proportions will be used for the evaluation of categorical (qualitative) data, and tabulations of descriptive statistics will be used to analyse continuous (quantitative) data. Safety endpoints (adverse events, laboratory parameters and vital signs) will be assigned to the following treatments for analyses based on the AE onset time (concept of treatment emergent AEs) or the planned time of the laboratory parameters and vital signs. the data recorded prior to first intake of dabigatran will be assigned to 'screening', and those between first intake of dabigatran until first idarucizumab intake will be assigned to 'dabigatran period', and those between first intake of idarucizumab until the EOT visit will be assigned to 'dabigatran + treatment', and those between EOT visit until the end of trial (FU2 visit) will be assigned to 'post- treatment', and those after the end of trial visit examination will be assigned to 'post-study'.

Adverse events will be coded using the Medical Dictionary for Regulatory Activities (MedDRA). Frequency, intensity and causal relationship of AEs will be tabulated by treatment, primary system organ class and preferred term. Serious and other significant AEs will be listed separately.

Descriptive statistics of laboratory values and those for the differences from baseline will be calculated. Frequency tables of changes with respect to the reference range between baseline and post-baseline value will also be presented.

Descriptive statistics for vital signs (blood pressure and pulse rate) will be calculated.

Details will be described in the TSAP.

7.3.5 Pharmacokinetic and pharmacodynamic analyses

7.3.5.1 Pharmacokinetic analyses

The pharmacokinetic parameters listed in [Section 5.4.1](#) will be calculated according to the Boehringer Ingelheim SOP "Standards and processes for analyses performed

within Clinical Pharmacokinetics/Pharmacodynamics" and given in [Appendix 10.1](#).

Only concentration values within the validated concentration range and actual sampling times will be used for the calculation of pharmacokinetic parameters. Concentrations used in the pharmacokinetic calculations will be in the same format provided in the bioanalytical report, that is, to the same number of decimal places provided in the bioanalytical report.

The following descriptive statistics will be calculated for analyte concentrations as well as for all pharmacokinetic parameters: N, arithmetic mean, standard deviation, minimum, median, maximum, arithmetic coefficient of variation, geometric mean, and geometric coefficient of variation. The data format for descriptive statistics of concentrations will be identical with the data format of the respective concentrations. The descriptive statistics of pharmacokinetic parameters will be calculated using the individual values with the number of decimal places as provided by the evaluation program. Then the individual values as well as the descriptive statistics will be reported with 3 significant digits in the clinical trial report.

Pharmacokinetic analyses will be performed using validated software programs, normally. Phoenix Winnonlin (Pharsight®) with applications validated for the respective purpose. Graphs and tables will be generated using validated customised SAS® macros or appropriate graphic software. A reference to the software used, e.g., name, will be indicated in the clinical trial report.

7.3.5.2 Pharmacodynamic analyses

The PD parameters listed in [Section 5.6.1](#) will be calculated according to the Boehringer Ingelheim SOP "Standards and processes for analyses performed within Clinical Pharmacokinetics/Pharmacodynamics".

The following descriptive statistics will be calculated as well as for all PD parameters: N, arithmetic mean, standard deviation, minimum, median, maximum, arithmetic coefficient of variation, geometric mean, and geometric coefficient of variation. The data format for descriptive statistics of PD marker will be identical with the data format of the respective PD marker. The descriptive statistics of PD parameters will be calculated using the individual

values with the number of decimal places as provided by the evaluation program. Then the individual values as well as the descriptive statistics will be reported with 3 significant digits in the clinical trial report.

For the other parameters of interest [redacted] and dTT (Hemoclot® DTI assay), as well as for [redacted], ratio to baseline will be plotted versus time.

Reversal of dabigatran-mediated anticoagulation will be explored based on return of coagulation measurements into the normal range (i.e. below ULN), where feasible.

[REDACTED]. Similar investigations will be done for [REDACTED], if feasible. The definition of baseline will be based on pre-dose measurement(s) plus/minus an appropriate tolerance for the respective PD measurement. Details will further be specified in the TSAP.

7.3.5.3 Pharmacokinetic-Pharmacodynamic relationship analyses

Details will be further specified in the TSAP.

7.4 INTERIM ANALYSES

No interim analysis is planned.

7.5 HANDLING OF MISSING DATA

7.5.1 Safety

With respect to safety evaluations, it is not planned to impute missing values except for AE dates. These will be imputed according to BI standards.

7.5.2 Plasma concentration - time profiles

Drug concentration data identified with NOS (no sample available), NOR (no valid result), NOA (not analyzed), or NOP (no peak detectable) will be displayed as such and not replaced by zero at any time point (this rule also applies also to the lag phase, including the predose values). Drug concentration data identified with BLQ (below the lower limit of quantification) will be displayed as such and not replaced by zero at any time point (this rule also applies also to the lag phase, including the predose values) with the exception of both unbound dabigatran and unbound sum dabigatran. For this two analyte, data identified with BLQ following the administration of idarucizumab will be replaced with the lower limit of quantification, until measurable concentrations re-occur. The appropriate time frame will be decided by the TCPK and described in the CTR.

Descriptive statistics of concentrations at specific time points will be calculated only when at least 2/3 of the individuals have concentrations within the validated concentration range. The overall sample size to decide whether the “2/3 rule” is fulfilled will be based on the total number of samples intended to be drawn for that time point (i.e. BLQ, NOR, NOS, NOA, NOP are included).

7.5.3 Pharmacokinetic parameters

For the noncompartmental analysis to idarucizumab and dabigatran, concentration data identified with NOS, NOR or NOA will generally not be considered. Concentration values in the lag phase identified as BLQ or NOP will be set to zero. All other BLQ/NOP values of the profile will be ignored.

The lag phase is defined as the period between time zero and the first time point with a concentration above the quantification limit. BLQ values for unbound dabigatran and unbound sum dabigatran data will be handled exceptionally; BLQ values will be replaced by the lower limit of quantification which is defined as 1 ng/mL.

If the predose concentration of the first administration is less than or equal to 5% of C_{max} value in that subject, the subject's data without any adjustments can be included in all pharmacokinetic measurements and calculations (i.e. the predose value will not be changed to zero). If the predose value is greater than 5% of C_{max} , the subject should be dropped from all statistical evaluations. The individual pharmacokinetic parameters can be calculated and listed separately. Every effort will be made to include all concentration data in an analysis. If not possible, a case to case decision is required whether the value should only be excluded from half-life estimation or the complete analysis.

- If a concentration is only excluded from half-life determination, it will be used for all other calculations (e.g. descriptive statistics) and for graphical presentation.
- If a concentration value is excluded from all calculations, it will not be presented graphically or used for the calculation of descriptive statistics and parameter determination. However the excluded concentration itself will be listed in the clinical trial report associated with an appropriate flag.

Descriptive statistics of parameters are calculated only when at least 2/3 of the individual parameter estimates of a certain parameter are available. If the actual sampling time will not be recorded or will be missing for a certain time point, the planned time will generally be used for this time point instead. Pharmacokinetic parameters which cannot be determined will be identified by "not calculated" (NC).

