5.4.1 Assessment of Pharmacokinetics

The following PK parameters will be determined for idarucizumab, if feasible:

- C_{\max} (maximum measured concentration of the analyte in plasma)
- [REDACTED]
- $AUC_{0-\infty}$ (area under the concentration-time curve of the analyte in plasma over the time interval from 0 extrapolated to infinity)

The following PK parameters will be determined for idarucizumab, if feasible:

- $Ae_{t_1-t_2}$ (amount of analyte eliminated in urine from the time point t_1 to time point t_2)

[REDACTED]

In addition, the following dose normalised parameters will be calculated for idarucizumab:

[REDACTED]

Additional pharmacokinetic parameter for idarucizumab may be calculated as appropriate.

In addition, the following PK parameters will be determined for unconjugated dabigatran, sum dabigatran, unbound dabigatran, unbound sum dabigatran and active dabigatran (calculated from dTT (Hemoclot® DTI assay), if feasible:

[REDACTED]

- $AUC_{t1-t2,ss}$ (area under the concentration-time curve of the analyte in plasma over the time interval from $t1$ to $t2$ at steady state)

[REDACTED]

Further, the following pre-dose concentrations will be determined for sum dabigatran, if feasible:

[REDACTED]

Further, the following PK parameter will be determined for unconjugated dabigatran and sum dabigatran, if feasible:

- $Ae_{t1-t2,ss}$ (amount of analyte eliminated in urine at steady state from the time point t_1 to time point t_2)

In addition, for unbound dabigatran, unbound sum dabigatran

[REDACTED]
[REDACTED]
[REDACTED]
[REDACTED]

Further, the following PK parameter will be determined for active dabigatran, if feasible:

[REDACTED]
[REDACTED]

Additional pharmacokinetic parameters for unconjugated dabigatran, sum dabigatran, unbound dabigatran, unbound sum dabigatran and active dabigatran may be calculated as appropriate.

Urine parameters will only be calculated as feasible for the analytes measured in urine, i.e. idarucizumab, as well as unconjugated and sum dabigatran.

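### The BLQ exception leaves out dTT-derived active dabigatran, so its Day 11 AUC may be bridged across the reversed period or not calculable (minor; no primary or secondary endpoint affected)

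*Protocol*

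**What the plan says.** Protocol 5.4.1 lists the dabigatran measures for which PK parameters are planned. The list ends with "unbound sum dabigatran and active dabigatran (calculated from dTT (Hemoclot® DTI assay), if feasible", and the parameters include a partial AUC at steady state. No time window or study day is given there for active dabigatran.

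Protocol 7.5.3 sets the rules for the noncompartmental analysis. BLQ values in the lag phase become zero; for the rest, "All other BLQ/NOP values of the profile will be ignored". The lag phase ends early: "The lag phase is defined as the period between time zero and the first time point with a concentration above the quantification limit".

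There is one exception: "BLQ values for unbound dabigatran and unbound sum dabigatran data will be handled exceptionally". For these two analytes, "BLQ values will be replaced by the lower limit of quantification which is defined as 1 ng/mL". Protocol 7.5.2 makes the matching exception for concentration profiles after idarucizumab, again "with the exception of both unbound dabigatran and unbound sum dabigatran". Protocol 7.3.5.1 adds: "Only concentration values within the validated concentration range and actual sampling times will be used for the calculation of pharmacokinetic parameters".

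SAP 6.6.2 and 6.6.3 send missing PK and PD data to an internal standard. SAP 4 declares no change from the protocol's methods.

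**The concern.** The exception exists because idarucizumab removes free drug abruptly, so that BLQ values in mid-profile carry information: the drug is gone. Active dabigatran, back-calculated from a clotting time, should behave in the same way, because a normal dTT corresponds to the bottom of its scale. Unconjugated and sum dabigatran do not need the exception, since Protocol 5.4.3.2 defines them as total drug in plasma.

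Without the exception, the low values that show reversal are discarded. A subject whose drug reappears late receives an AUC drawn through the reversed period as if concentrations had declined smoothly. A subject in whom it never reappears has no AUC. Both effects work against the best-reversed subjects, and a Day 11 to Day 4 comparison of this parameter would understate the effect of idarucizumab.

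**Working it through.** The documents give no figure on this point, so there is nothing to reproduce. The check applies the protocol's own rules to its own sampling times.

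**Inputs from the documents**
- dTT sampling on Day 11 (Flow Chart 2, Part 2): 240:00, 241:00, 241:55, 242:00, 242:05, 242:15, 242:20, 243:20, 244:00, 246:00, 248:00, 252:00, 254:00, 266:00, 290:00 and 314:00. Measured from the morning dabigatran dose at 240:00, 241:55 is 1.917 h, 243:20 is 3.333 h and 252:00 is 12 h.
- The first idarucizumab infusion starts about 1 h 55 min after that dose (Protocol 6.2.2).
- AUC rule (Protocol Appendix 10.1): linear when rising, logarithmic when falling.
- Parameter summaries need at least 2/3 of the individual estimates (Protocol 7.5.3); 12 subjects are planned (Protocol 7.7).

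**Assumptions, not in the documents**
- Values after reversal are reported as BLQ.
- The window is 2-12 h, borrowed from the secondary endpoint for unbound sum dabigatran.
- Active dabigatran is 200 ng/mL at 1.917 h and 20 ng/mL at 12 h.

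**Step 1: which rule applies.** Samples at 241:00 and 241:55 precede the infusion, at or near dabigatran steady state, and should be measurable. Later BLQ values are therefore not lag phase, and active dabigatran is not in the exception. They are ignored.

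**Step 2: every value between is BLQ.**
- Slope: ln(200/20)/(12 − 1.917) = 0.2284 per h.
- Interpolated value at 2 h: 200 × exp(−0.2284 × 0.0833) = 196.2.
- AUC2-12 = (196.2 − 20)/0.2284 ≈ **772 ng·h/mL**.

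**Step 3: one value of 20 ng/mL is measured at 243:20.**
- Slope to that point: ln(10)/(3.333 − 1.917) = 1.625 per h; value at 2 h = 174.7.
- 2 to 3.333 h: (174.7 − 20)/1.625 = 95.2.
- 3.333 to 12 h: 20 × 8.667 = 173.3.
- AUC2-12 ≈ **268 ng·h/mL**.

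**Step 4: LLOQ substitution in the Step 2 case.** With LLOQ L, the area is 6L for 2-8 h plus 4 × (L + 20)/2 for 8-12 h, that is 8L + 40. This gives 120 for L = 10 and 200 for L = 20. Bridging is then 772/120 = 6.4 times or 772/200 = 3.9 times the substituted value. In the Step 3 case with L = 20, it is 268/200 = 1.3 times.

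**Step 5: scale.** A mono-exponential fall from 200 ng/mL at 2 h, with the 12-17 h terminal half-life in Protocol 1.2, gives an AUC2-12 of 1519-1642. Step 2 is 47-51% of that; Step 3 is 16-18%. The early decline may be faster than the terminal one, so this reference is rough.

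**Step 6: nothing returns.** The last usable point, 1.917 h, lies before the window, so AUC2-12 is not calculable. The 2/3 rule needs 8 of 12 estimates, so five such subjects suppress the Day 11 summary. If each subject independently has probability 0.2, 1/3 or 0.5 of this, the chance of five or more is 0.07, 0.37 or 0.81.

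Over a wider grid (start 100-300 ng/mL, LLOQ 1, 5 or 20 ng/mL, return at 1.5 times the LLOQ at 8 to 26 h, all earlier post-infusion values BLQ), ignoring BLQ inflates the AUC 1.9-fold to 119-fold. The direction never changes; the size is set by the assumptions.

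**The case against.** The strongest reply is that little depends on this parameter. It is neither primary nor secondary, is planned only if feasible, and everything is descriptive (Protocol 7.2). A reader might infer that the trial's functional measure of reversal is wrong. The documents do not support that. The primary PD endpoint is calculated from dTT ratios (SAP 7.4), and reversal is judged by dTT against an upper limit of normal (SAP 6.7); neither uses a concentration LLOQ. The secondary AUC, for unbound sum dabigatran, is covered by the exception. This part of the reply stands and sets the severity.

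The premise is also not documented. No visible text says that dTT-derived values are flagged BLQ or gives their LLOQ. Parts of Protocol 5.4.1 and 5.6.3 are blacked out, and the internal standard is not available. That stands as a condition on the finding. It does not remove the finding, because a general standard would have to override an explicit protocol sentence while SAP 4 declares no change.

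A reader might also infer that the Day 11 AUC would be about half or more of the Day 4 value. That holds only if every sample up to 12 h or later is BLQ. Several samples fall between, and one measurable value shortens the bridge sharply (Step 3).

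Finally, the not-calculated label and the 2/3 rule make a missing AUC visible. They do nothing about a bridged AUC, which is reported as an ordinary number.

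**Conclusion.** The gap is real and minor. As written, the BLQ rules treat active dabigatran differently from the two unbound analytes, although the reason for the exception applies equally. If dTT-derived values are reported as BLQ after idarucizumab, the Day 11 AUC is biased upward or lost, selectively in well-reversed subjects.

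No single figure for the size can be defended. It turns on the unstated LLOQ and on how many consecutive samples are BLQ, and the 2-12 h window and Day 11 use are themselves inferred for this analyte.

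**What to change.** In Protocol 7.5.2 and 7.5.3, or in SAP 6.6.2, add active dabigatran to the analytes whose BLQ values after idarucizumab are replaced by the LLOQ. Use the LLOQ of the dTT-based assay, and state it, rather than the 1 ng/mL defined for the unbound analytes. Label the resulting Day 11 AUC an upper bound.

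The cost is a phrase in two paragraphs; sampling, assays and the other analytes are unchanged. The downside is small: when all values from 2 to 12 h are BLQ, the AUC becomes a conservative ceiling of about 10 × LLOQ, for example 50 ng·h/mL at an assumed LLOQ of 5 ng/mL.

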7.6 RANDOMISATION

Not Applicable, as only 1 dose group is planned

7.7 DETERMINATION OF SAMPLE SIZE

It is planned to include a total of 12 subjects in this trial. The planned sample size is not based on a power calculation. A group size between 8 and 12 per dose level is commonly used in

healthy subject trials and is considered sufficient for exploratory investigation of single/multiple dose safety and pharmacokinetics.

8. INFORMED CONSENT, TRIAL RECORDS, DATA PROTECTION, PUBLICATION POLICY

The trial will be carried out in compliance with the protocol, the ethical principles laid down in the Declaration of Helsinki, in accordance with the ICH Harmonized Tripartite Guideline for Good Clinical Practice (GCP), relevant BI Standard Operating Procedures (SOPs) and other relevant regulations.

Standard medical care (prophylactic, diagnostic and therapeutic procedures) remains in the responsibility of the treating physician of the subject.

The Investigator will inform the sponsor immediately of any urgent safety measures taken to protect the trial subjects against any immediate hazard, and also of any serious breaches of the protocol or of ICH GCP*.

The Boehringer Ingelheim transparency and publication policy can be found on the following web page: trials.boehringer-ingelheim.com. The rights of the Investigator and of the sponsor with regard to publication of the results of this trial are described in the Investigator contract. As a rule, no trial results should be published prior to finalization of the Clinical Trial Report.

The certificate of insurance cover is made available to the Investigator and the subjects, and is stored in the ISF (Investigator Site File).

8.1 TRIAL APPROVAL, PATIENT INFORMATION, INFORMED CONSENT

This trial will be initiated only after all required legal documentation has been reviewed and approved by the respective Institutional Review Board (IRB) / Independent Ethics Committee (IEC) and competent authority (CA) according to national and international regulations. The same applies for the implementation of changes introduced by amendments.

Prior to subject participation in the trial, written informed consent must be obtained from each subject (or the subject's legally accepted representative) according to ICH / GCP and to

the regulatory and legal requirements of the participating country. Each signature must be personally dated by each signatory and the informed consent and any additional subject-information form retained by the Investigator as part of the trial records. A signed copy of the informed consent and any additional subject information must be given to each subject or the subject's legally accepted representative.”

Re-consenting may become necessary when new relevant information becomes available and should be conducted according to the sponsor's instructions.

The consent and re-consenting process should be properly documented in the source documentation.

8.2 DATA QUALITY ASSURANCE

A quality assurance audit/inspection of this trial may be conducted by the sponsor, sponsor's designees, or by IRB / IEC or by regulatory authorities. The quality assurance auditor will have access to all medical records, the Investigator's trial-related files and correspondence, and the informed consent documentation of this clinical trial.

8.3 RECORDS

Case Report Forms (CRF) for individual subjects will be provided by the sponsor. For drug accountability, refer to [Section 4.1.8](#).

8.3.1 Source documents

In accordance with regulatory requirements the Investigator should prepare and maintain adequate and accurate source documents and trial records that include all observations and other data pertinent to the investigation on each trial subject. Source data as well as reported data should follow good documentation practices and be attributable, legible, contemporaneous, original and accurate. Changes to the data should be traceable (audit trail).

Data reported on the CRF must be consistent with the source data or the discrepancies must be explained.

The current medical history of the subject may not be sufficient to confirm eligibility for the trial and the Investigator may need to request previous medical histories and evidence of any diagnostic tests. In this case the Investigator must make three documented attempts to retrieve previous medical records. If this fails a verbal history from the subject, documented in their medical records, would be acceptable.

Before providing any copy of subjects' source documents to the sponsor the investigator must ensure that all subject identifiers (e.g. subject's name, initials, address, phone number, social security number) have properly been removed or redacted to ensure subject confidentiality.

If the subject is not compliant with the protocol, any corrective action e.g. re-training must be documented in the subject file.

For the CRF, data must be derived from source documents, for example:

- Subject identification: gender, date or year of birth (in accordance with local laws and regulations)
- Subject participation in the trial (substance, trial number, subject number, date subject was informed)
- Dates of Subject's visits, including dispensing of trial medication
- Medical history (including trial indication and concomitant diseases, if applicable)
- Medication history
- Adverse events and outcome events (onset date (mandatory), and end date (if available))
- Serious adverse events (onset date (mandatory), and end date (if available))
- Concomitant therapy (start date, changes)
- Originals or copies of laboratory results and other imaging or testing results, with proper documented medical evaluation (in validated electronic format, if available)
- Completion of Subject's Participation in the trial" (end date; in case of premature discontinuation document the reason for it).
- Prior to allocation of a subject to a treatment into a clinical trial, there must be documented evidence in the source data (e.g. medical records) that the trial participant meets all inclusion criteria and does not meet any exclusion criteria. The absence of records (either medical records, verbal documented feedback of the subject or testing

conducted specific for a protocol) to support inclusion/exclusion criteria does not make the subject eligible for the clinical trial.

